4.2 Exclusion Criteria

To be eligible for study enrollment, potential study patients must not meet any of the following exclusion criteria:

1. Any indwelling vascular catheter (including that used for dialysis) or anticipated of use of an indwelling catheter anytime during the study (including the Initial Screening and Full Screening Periods).

Patients for whom a central venous catheter is used within 2 weeks prior to Step 2 of the Initial Screening Period (blood draw for IL-6, see [Section 5.2](#)) will be also be considered screening failures.

2. Use of systemic immunosuppressive drugs during the Full Screening Period or anticipated use of such drugs any time during the study.

Note: Use of otic, ophthalmic, inhaled, and topical corticosteroids or local corticosteroid injections are not exclusionary. Oral prednisone up to 5 mg per day (or equivalent) is permitted.

3. Clinical evidence or suspicion of active or smoldering infection (e.g., diabetic foot ulcer) or use of systemic antibiotics, systemic antivirals, or systemic antifungals within 2 weeks prior to Step 2 of the Initial Screening Period (blood draw for IL-6, see [Section 5.2](#)), during the Initial Screening Period, or the Full Screening Period.

(“Systemic” is defined as oral or intravenous drugs that are absorbed into the circulation.)

4. Hospitalization or outpatient procedures within 2 weeks prior to Step 2 of the Initial Screening Period (blood draw for IL-6, see [Section 5.2](#)), during the Initial Screening Period, or the Full Screening Period unless approved by the Medical Monitor.

Note: Please contact the Medical Monitor for approval and determination of timing of IL-6 measurements if considering enrolling patients with hospitalizations or outpatient procedures during this time frame.

5. Inability to undergo a non-contrast magnetic resonance imaging (MRI) scan (e.g., weight over the limits for MRI machine, claustrophobia that cannot be managed, certain metallic indwelling foreign bodies). Requirement for MRI may be exempted by the medical monitor due to practical considerations. In such situations, patients may be enrolled even if they are unable to undergo MRI.
6. Positive tuberculosis blood test at Screening
7. Evidence of HIV-1 or HIV-2 infection by serology at Screening.
8. Hepatitis B or C by serology (i.e. Hepatitis B Surface Antigen or Hepatitis C antibody positive) at Screening.
9. AST or ALT > 2.5x ULN at Screening.
10. History of liver cirrhosis or home oxygen use (other than nocturnal-only oxygen for those with sleep apnea).
11. History of gastrointestinal ulceration or active diverticulitis in the 1 year prior to Initial Screening.

12. Absolute neutrophil count $< 2.0 \times 10^9/L$ at Initial and Full Screening.
13. Platelet count $< 100 \times 10^9/L$ at Initial and Full Screening.
14. Expected to receive any investigational drug or any of the exclusionary drugs listed in [Appendix B](#) during the Treatment Period or Safety Follow-Up Period.
15. Received an investigational drug within 30 days prior to the start of the Full Screening Period.
16. Known allergy to the Study Drug or any of its ingredients.
17. Currently breastfeeding
18. Any condition that could interfere with, or for which the treatment might interfere with, the conduct of the study or interpretation of the study results, or that would in the opinion of the Investigator increase the risk of the patient's participation in the study. This would include but is not limited to alcoholism, drug dependency or abuse, psychiatric disease, epilepsy, anemia attributable to a primary hematologic disease (e.g., sickle cell anemia), or any unexplained blackouts.
19. Actively treated or active malignancy (other than non-melanoma skin cancers or cervical carcinoma in situ considered cured at the time of Full Screening) during the 1 year prior to Full Screening.
20. Myocardial infarction during the 2 months prior to Full Screening or during Screening.
21. Known or suspected occult or active bleeding other than that related to the hemodialysis procedure.
22. Received a red blood cell or whole blood transfusion within 2 months prior to Full Screening or anticipated to receive a blood transfusion at any time during the study.
23. Have inflammatory bowel disease that has been clinically active during the 3 months prior to Full Screening or bone marrow or organ transplant.

Note: Patients with a previously explanted kidney transplant are eligible as are those who have an implanted kidney transplant, but have not received immunosuppression for at least 6 months prior to Full Screening.
24. Anticipated to receive an organ transplant during the time frame of the study.
25. iPTH at Screening > 2500 pg/mL.

4.3 Criteria for Discontinuation of Study Drug

Study Drug may be prematurely discontinued for a number of reasons, including:

- An intercurrent illness
- Any intolerable AE that cannot be ameliorated by appropriate medical intervention or that in the opinion of the Medical Monitor or Investigator would lead to undue risk if the patient were to continue on treatment

- Implementation of stopping rules (see [Section 4.4](#))
- Pregnancy
- Organ transplantation or development of another indication for chronic immunosuppression,
- Withdrawal of consent. A patient may elect to withdraw consent to treatment at any time.
 - Patients discontinuing Study Drug treatment after receiving any amount of Study Drug should undergo all follow-up study procedures unless the patient also explicitly withdraws consent for these procedures. The Study Drug has a long pharmacodynamic effect; therefore, continued monitoring for pharmacodynamic effects and safety is prudent. Patients withdrawing their consent for all study procedures must be given the option to continue to give consent for passive follow-up (i.e., by means of chart review) for adverse events through Study Week 24.

Reasons for all withdrawals/discontinuations of Study Drug will be recorded, and the Medical Monitor should be informed of all such cases as they occur.

4.4 Dose-Limiting Toxicities, Maximum Tolerated Dose, and Stopping Rules

Prior to dose escalation (i.e., higher total dose than studied in the preceding cohorts), there will be a formal safety review by the Safety Review Committee. The safety review required for dose escalation will include 21 days of treatment data from the preceding cohort(s).

Dose-Limiting Toxicities are defined as follows:

1. Confirmed Grade 3 neutropenia and representing a decline of > 25% from baseline
2. Serious adverse events of infection in the presence of confirmed Grade 2 or higher new onset lymphopenia or new onset neutropenia.
3. \geq Grade 3 ALT or AST
4. \geq Grade 4 hematologic toxicity
5. \geq Grade 3 non-hematologic toxicity

DLT will be defined as any toxicity the relationship of which to the investigational agent cannot be ruled out as follows:

- With the exception of Grade 3 non-hematologic events, Grade 3 (or higher) CTCAE toxicity of above events having an assessed relationship to the Study Drug of “definitely”, “probably”, “possibly”, or “unlikely” will be considered DLTs.

Note: “non-hematologic events” refer to DLT criteria 1, 2, 3, and 5 above.

- Grade 3 non-hematologic toxicities having an assessed relationship to the Study Drug of “definitely”, “probably” or “possibly” will be considered DLTs.

In addition, dose-escalation may be halted for any safety trend believed to be dose-related that would pose an unacceptable risk if dose were escalated.

If more than 2 of 8 COR-001-treated patients in a cohort experience a DLT, the MTD will be exceeded and stopping criteria for that dose will have been met.

In addition, if 1 of 8 COR-001-treated patients in a cohort experiences a Grade 4 or 5 DLT, the dose will not be escalated.

Stopping Rules for Individual Patients

Severe (i.e., \geq Grade 3): infusion-related reactions, cardiopulmonary infusion reactions, anaphylaxis, or hypersensitivity (see [Section 8.2](#))

Stopping Rules for the Entire Study

If ≥ 5 COR-001-treated patients develop anaphylaxis at any point during the entire study, enrollment and further dosing will be stopped.

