3.2 Study Schematic

Figure 2 Dose Escalation Schematic

- ¹ If the MTD is not exceeded, dose escalation may continue.
- ² If the MTD is exceeded, a lower dose, including previously studied dose, may be selected.

The MTD assessment will be based on safety data from Weeks 1 to 3. If more than 2 of 8 active patients in a cohort experience a DLT, the MTD will be considered to have been exceeded.

The planned doses shown here may be adjusted based on accruing PK, PD, and safety data. The highest dose that will be studied is a cumulative dose of 360 mg. Expansion cohorts to further evaluate doses below the dose that exceeded the MTD may be initiated at any time.

The randomization ratio within each cohort will be 8:2 (COR-001 to placebo).

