3.5.4 Rationale for the Dose Regimens

The main goal of COR-001 dosing in the planned Phase 1/2 hemodialysis patient study is to attain and maintain serum COR-001 concentrations sufficient for $\geq 90\%$ IL-6 binding over the 3-month Treatment Period, with a secondary goal of reducing hsCRP to below 5 mg/L while keeping the highest planned dose more than 20-fold below the no adverse effect level (NOAEL) observed in primates.

Effects on IL-6 and hsCRP

Pharmacokinetic and PD models were created based on data from the Phase 1 trial in RA patients (Study D4430C00001) and used to simulate dosing regimens that achieve the above goals (Section 3.5.4). Based on these models, lower doses were needed to maintain serum COR-001 concentrations above the target value (i.e., that value required to achieve $> 90\%$ IL-6 binding) compared to those needed to normalize hsCRP (defined as $\text{hsCRP} < 5\text{mg/L}$) in a hypothetical hemodialysis population whose baseline hsCRP is at median and serum IL-6 level is above the median. hsCRP normalization in at least 1/3 patients is predicted for cumulative COR-001 dose of ≥ 12 mg, and is not predicted for all patients until cumulative doses of 60 mg or greater are achieved. The COR-001 dose regimens planned are itemized below. Lower doses (including previously studied doses) may be substituted for the planned doses in the table below based on accruing data. In addition, PK and PD results will be reviewed to assess the appropriateness of the next planned dose and to guide revision of the next dose to be evaluated, if necessary.

Dose Cohort	Dose Regimen	Number of Doses	Total Cumulative Dose
1	2 mg every 14 days	6	12 mg
2	6 mg every 14 days	6	36 mg
3	20 mg every 14 days	6	120 mg
4	60 mg every 14 days	6	360 mg

The planned doses all provide plasma IL-6 binding in excess of 90% for the duration of the study, while hsCRP normalization is expected to be attained in 1/3 of patients at the lowest dose, and in 3/3 patients at the highest dose. Full suppression of hsCRP is not believed to be required for beneficial effect on hematologic or iron parameters given the linear correlation between CRP and the degree of erythropoietic inefficiency (Bárány 1997).

As of Amendment 3, the actual doses (all given every 14 days) were 2 mg (Cohorts 1 and 4); 6 mg (Cohorts 2 and 3); 20 mg (Cohort 5).

Safety Margins

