Available data for anti-IL6R (tocilizumab) and anti-IL6 (siltuximab) therapies suggest neutralization of IL-6 have acceptable safety and tolerability profiles for the indications studied. Infusion-related and life-threatening hypersensitivity reactions are rare with these agents. Anti-inflammatory therapies in general run the risk of inducing immune suppression and promoting the emergence of infections, sometimes serious in nature. Although anti-IL-6 therapies lower neutrophil counts and may induce frank neutropenia, their rates of infectious complications appear to be similar to other immune-modulatory biologic agents when accounting for patient-specific factors ([Sakai 2015](#), [Sanofi 2016](#)). Gastrointestinal perforation has been associated with anti-IL-6 therapy, however data suggests proper exclusion criteria may mitigate these risks ([Tanaka 2014](#)).

The inclusion and exclusion criteria and monitoring schema employed in the planned clinical studies are designed to minimize and manage the potential risks of COR-001 therapy as inferred from other anti-IL-6 therapies. The exclusion of patients with known infection, the use of absolute-neutrophil count stopping rules, prohibition of the use of live vaccines and certain concomitant medications which are metabolized by the CYP system and display narrow therapeutic windows, exclusion of patients with a history of diverticulosis, as well as the use of the CTCAE system of adverse event reporting and maximum tolerated dose definition are designed to minimize the drug-associated risks to study patients.

COR-001 will be administered in a monitored setting (the hemodialysis unit) where frequent laboratory measurements (to ascertain for effects such as altered liver function and elevation in serum cholesterol) and close contact with dialysis staff will allow for prudent monitoring and early treatment of complications should they occur.

Finally, the use of a mechanistically-derived genotype patient selection strategy is intended to enrich the enrolled cohort for patients with the greatest likelihood of response to anti-IL-6 therapy. Therefore, the treatment is precisely targeted to the population who might benefit the most.

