12 STUDY COMMITTEES AND COMMUNICATIONS

After all patients in a cohort have completed 21 days of treatment (or last visit, if prematurely discontinued), the SRC will evaluate the safety and tolerability of COR-001 and recommend the next dose. The SRC may not be convened if the next cohort is expected to be the last cohort in the study. Pharmacokinetic data, as it becomes available, will also be made available to the SRC. The Safety Review Committee will apply its judgment to the conduct of this study in order to ensure the safety of study participants.

The SRC will consist of the following core members:

- Two or more clinicians, at least one of whom is a nephrologist with expertise in clinical trial safety data review
- A statistician (non-voting member)

The full activities and responsibilities of the SRC are described in the SRC charter.

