- [6] Obtain weight within 30 minutes prior to the start of dialysis and within 30 minutes after the end of dialysis for the **same** dialysis session during which Lab Panel 8 [CARD] was collected.
- [7] Net ultrafiltration volume should be recorded for the **same** dialysis session during which Lab Panel 8 [CARD] data were collected.
- [8] Have patient complete the FACIT-F questionnaire (see instructions in Study Reference Manual) prior to dialysis or during the first hour of dialysis
- [9] Limited physical exam to include skin, oropharynx, lungs, heart, abdomen, extremities (including feet), and any areas suggested by symptoms, with particular attention to signs of infection. May be performed by a physician-investigator or mid-level provider. Record abnormal findings in the source documents.
- [10] Perform any time prior to starting dialysis.
- [11] Only adverse events considered related to study procedures.
- [12] All adverse events are collected starting with the signing of the Long ICF.

Schedule of Events for the Treatment Period – Weeks 1 through 6

Treatment Period							
Study Week(s)	1		2	3	4	5	6
Visit Window		+1	±2	±2 ¹⁴	±2	±2 ¹⁴	±2
Study Day(s)	1 [M-Th, if possible]	3 5	8	15	22	29	36
	ESA and iron dosing per Appendix C						
Randomization	X [15]						
Study Drug Administration [1]	X			X		X	
Lab Panel 1 [CHEM]	X [a]						X [a]
Lab Panel 2 [LIP], Lp(a), serum pregnancy [2]	X [a]						X [a]
Lab Panel 3 [INFL1]	X [a]			X [a]	X [a]		
Pre-Albumin, hsCRP	X [a]	X[a,d]	X [a,d]	X [a,b]	X [a]	X [a]	X [a]
Lab Panel 4 [SPRBC]	X [a]		X [a]	X [a]	X [a]	X [a]	X [a]
Lab Panel 5 [HEME]	X [a]		X [a]	X [a]	X [a]	X [a]	X [a]
Lab Panel 6 [IRON]	X [a]		X [a]	X [a]	X [a]	X [a]	X [a]
Lab Panel 7 [PK]	X [a,b,c]	X[a,d]	X [d]	X [a,b]		X[a]	
Lab Panel 8 [CARD]							
Lab Panel 10 [ADA]	X [a]			X [a]		X [a]	
Lab Panel 11 [INFL2]	X[a,b,c]	X[a,d]	X [d]	X [a,b]		X[a]	
Lab Panel 12 [BIO]	X [a]						
Serum pregnancy [2]	X [a]						
Local Lab INR [3]	X [a]		X [a]	X [a]	X [a]	X [a]	X [a]
12-lead ECG pre-dialysis	X						X
FACIT-F [13]	X						X
Limited Physical Examination [5]							X
Vital Signs	X[7]		X[6]	X[7]	X[6]	X[7]	X[6]
Weight (pre-dialysis)							
Weight (post-dialysis)							
Record net ultrafiltration during dialysis							
Cardiac MRI							
Hand grip strength	X [11]						X [11]
Adverse Events	X						
Concomitant Medications	X						

Schedule of Events for the Treatment Period – Weeks 7 through 12/ET-1

Treatment Period (continued)							

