Appendix D Laboratory Measurements

Laboratory	Panel Name	Tests Included
Central	Panel 1: Chemistry [CHEM]	Sodium, potassium, chloride, bicarbonate (or CO ₂), calcium, phosphate, alanine aminotransferase (ALT), aspartate aminotransferase (AST), blood urea nitrogen (BUN) creatinine, total bilirubin, direct bilirubin, alkaline phosphatase, albumin, glucose
Central	Panel 2: Lipids [LIP]	Total cholesterol, low density lipoprotein (LDL) cholesterol, high density lipoprotein (HDL), triglycerides
Central	Panel 3: Inflammation 1 [INFL1]	serum amyloid A, hepcidin
Central	Panel 4: Special RBC Indices [SPRBC]	reticulocyte hemoglobin concentration (CHr), % hypochromic red cells (%HRC)
Central	Panel 5: Hematology [HEME]	Hemoglobin, hematocrit, reticulocyte count, red blood count (RBC) indices (e.g., mean corpuscular volume (MCV), red cell distribution width (RDW), platelets, white blood count (WBC), WBC differential
Central	Panel 6: Iron Indices [IRON]	TSAT, ferritin, iron, total iron binding capacity (TIBC)
Central	Panel 7: PK [PK]	COR-001
Central	Panel 8: Cardiac Markers [CARD]	Troponin T, NT-proBNP
Central	Panel 9: Infection Screen [INFEC]	HIV 1 and 2, Hepatitis B surface antigen, Hepatitis B surface antibody, Hepatitis C antibody, mycobacterium tuberculosis blood test (i.e., interferon gamma release assay)
Central	Panel 10: Anti-Drug Antibodies [ADA]	Anti-COR-001 binding antibodies and neutralizing antibodies (if binding antibodies are detected)
Central	Panel 11: Inflammation 2 [INFL2]	Total and free IL-6
Central	Panel 12: Future biomarkers [BIO]	Future cardiac, renal, and hematologic markers, including gene variations, ribonucleic acid, or protein markers
Central	Panel 13: B-Vitamins [BVIT]	B-12, folate
Central	Other individual tests	Screening (total) IL-6, genotype, intact parathyroid hormone [PTH], lipoprotein a [Lp(a)], pregnancy [β -hCG in women of childbearing potential only], follicle-stimulating hormone (FSH), stool occult blood, pre-albumin, hsCRP
Local	Coagulation	International normalized ratio (INR) (warfarin-treated patients only)

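### No post-dose ALT or AST is scheduled before Day 36, so the Day 21 escalation review has no systematic data on its own liver DLT criterion

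*Protocol*

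**What the plan says.** The primary safety endpoint (Protocol 3.1.2, SAP 1.2.1) is to characterise the MTD, or to establish that the highest dose examined did not exceed it.

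- **Window.** Protocol 3.2: "The MTD assessment will be based on safety data from Weeks 1 to 3". Protocol 4.4: "The safety review required for dose escalation will include 21 days of treatment data from the preceding cohort(s". Section 12 times the committee review: "After all patients in a cohort have completed 21 days of treatment" (or made a last visit).
- **Criterion.** Item 3 of the DLT list in Section 4.4 is "Grade 3 ALT or AST", with the threshold read as Grade 3 or higher.
- **Rules.** More than 2 of 8 treated patients with a DLT means the MTD is exceeded. One Grade 4 or 5 DLT among 8 is enough to bar escalation.
- **Measurement.** Appendix D places "alanine aminotransferase (ALT), aspartate aminotransferase (AST), blood urea nitrogen (BUN) creatinine" in Panel 1, and no other panel or individual test lists ALT or AST. Section 10.2.5 limits local tests to INR and, if needed, stool occult blood.
- **Schedule.** In the Appendix A table for Weeks 1 to 6, the row "Lab Panel 1 [CHEM" is marked on Days 1 and 36 only, both pre-dialysis.
- **Detection.** SAP 8.1 has the sponsor find laboratory-based DLTs from laboratory listings and query them as adverse events. SAP 8.3 limits the DLT table to Study Days 1–21.
- **Risk mitigation.** Section 3.7 relies on "frequent laboratory measurements (to ascertain for effects such as altered liver function and elevation in serum cholesterol" in the dialysis unit.

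**The concern.** The plan treats liver toxicity as important enough to be a DLT criterion of its own, but schedules no test that could show it inside the DLT window. A transaminase elevation without symptoms is the kind of event that only a scheduled test finds reliably. If none is drawn, the listings in SAP 8.1 contain nothing to review, and the absence of liver DLTs by Day 21 reflects absence of measurement.

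The escalation decision and the MTD conclusion are both at stake. A single undetected Grade 4 ALT or AST DLT would be enough to let an escalation proceed that the rule would have stopped. A Grade 3 elevation first seen on Day 36 would also fall outside the SAP's DLT table. Other chemistry-based toxicities under criterion 5, such as bilirubin or potassium, share the gap. Blood-count and clinically evident DLTs do not.

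**Working it through.** **1. Where ALT and AST are measured.** Panel 1 only (Appendix D).

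**2. When Panel 1 is drawn.** The Weeks 1–6 row of Appendix A, set against the hematology panel and dosing:

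| Day | 1 | 3/5 | 8 | 15 | 22 | 29 | 36 |
|---|---|---|---|---|---|---|---|
| Panel 1 (ALT, AST) | X, pre-dialysis | – | – | – | – | – | X |
| Panel 5 (hematology) | X | – | X | X | X | X | X |
| Dose | X | – | – | X | – | X | – |

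Two checks show this is not a damaged table. The Amendment 3 log gives the previous serum albumin days as Week -2 and Days 1, 36, 78 and 162, and albumin is part of Panel 1. The ECG and FACIT-F rows have the same cell pattern, and Section 5.4.7 places both at Week 6.

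**3. Count inside the window.**
- Scheduled post-dose ALT/AST in Days 2–21: **0** per patient.
- Scheduled post-dose hematology in Days 2–21: 2 (Days 8 and 15).
- Earliest scheduled post-dose ALT/AST: 36 − 2 = Day 34. That is 34 − 21 = 13 days after the window closes, or 36 − 21 = 15 days at the nominal visit.
- Planned doses before that result: Days 1, 15 and 29, so 3.

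**4. The plan's own probabilities.** Protocol 11.1 takes 8 patients and a 25% DLT rate:
- P(at least 1) = 1 − 0.75⁸ = 0.900
- P(2 or more) = 1 − 0.75⁸ − 8(0.25)(0.75⁷) = 0.633

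Both stated figures (90% and above 63%) reproduce. They presume that every DLT that occurs is observed. As an illustration only, suppose the whole 25% were silent ALT/AST events and a fraction *c* came to light by unscheduled means. The observed rate is then 0.25*c*:

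| c (assumed) | P(at least 1 of 8 observed) | P(more than 2 of 8 observed) |
|---|---|---|
| 1 | 0.900 | 0.321 |
| 0.5 | 0.656 | 0.067 |
| 0.25 | 0.403 | 0.011 |
| 0 | 0 | 0 |

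**5. What a clean result can support.** If *k* treated patients have a post-dose result and none is Grade 3 or higher, the one-sided 95% upper bound on the rate is 1 − 0.05^(1/k):

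| k (assumed) | Upper bound |
|---|---|
| 8 | 31% |
| 4 | 53% |
| 2 | 78% |
| 0 | none |

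**6. Decisions already taken.** Protocol 3.5.4 gives the actual doses as "2 mg (Cohorts 1 and 4); 6 mg (Cohorts 2 and 3); 20 mg (Cohort 5" mg-level cohorts, so in cohort order 2, 6, 6, 2, 20 mg. Two escalations (2 to 6 mg and 6 to 20 mg) had been made by Amendment 3.

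**The case against.** The schedule itself is hard to dispute. The case against concerns consequence and remedy.

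- **Much of the reporting is already planned.** SAP 8.4 summarises laboratory values by visit, Grade 3 or higher non-hematology results, shifts to worst grade, and ALT/AST above 3× ULN. SAP 2.1 presents COR-001 by dosing regimen. This stands in part: a Day 36 elevation would be reported somewhere. But the Grade 3 summary is not stated to be per visit, and none of it supplies in-window data or qualifies the MTD conclusion.
- **The review is not sealed at Day 21.** Section 4.4 lets escalation be halted for any dose-related safety trend, and early enrollees may have Day 36 results when the committee meets. That needs a patient dosed about 13–15 days or more before the last in the cohort. With the order 2, 6, 6, 2, 20 mg, Day 36 data from the first 6 mg cohort could well have existed before 20 mg began. The documents give neither enrolment rates nor cohort dates, so this is possible but unproven, and it is not systematic.
- **There may be no cohort left to fix.** SAP 1.2.3 lists only 2, 6 and 20 mg, and SAP Section 11 ends at Cohort 6. The protocol still permits 60 mg. This stands as a real uncertainty, and the schedule change is conditional on a further escalation.
- **Section 3.7 may describe routine dialysis-unit care, not Appendix A.** That reading is fair, but it requires no ALT or AST by any given day.
- **Cohort size limits the inference anyway.** Even full testing of 8 leaves a 31% bound. True, but the one-event Grade 4 rule depends on detecting an individual event, not on estimating a rate.
- **Cost.** Amendment 3 shows concern about blood volume, and counting a Day 22 value alters the window between cohorts. The first point needs checking with the laboratory. On the second, a pre-dialysis Day 22 sample closes exactly 21 days of treatment, so counting it fits the rule's intent.

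**Conclusion.** The concern holds. Under the plan as written, DLT criterion 3 has zero scheduled post-dose observations per patient in the window on which the MTD is judged, and the first comes 13 to 15 days too late. This follows from Appendices A and D alone and needs no assumed event rate. The capture fractions and numbers tested shown above are assumptions that only illustrate the size.

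The effect is under-ascertainment of chemistry-detected DLTs. It does not invalidate the trial, and it leaves the clinical and hematologic criteria untouched. But a statement that a dose did not exceed the MTD should not imply that liver toxicity was systematically checked by Day 21. How many patients had an unscheduled, early termination or early Day 36 result in time for each review cannot be known from the documents, and the committee charter is not among them.

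**What to change.** **Any remaining escalation cohort.** Run ALT and AST on the pre-dialysis draws that already take place on Days 8, 15 and 22. Let the Day 22 (±2) result enter the committee's review and count as an in-window DLT value, so that the period after the Day 15 dose is covered. Amend the Appendix A chemistry row and the SAP's Day 1–21 DLT table to match.

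**Cohorts already dosed.** State that criterion 3 was not systematically assessed by Day 21. Beside the MTD conclusion, report by dose how many treated patients had a Day 36 ALT/AST and how many were Grade 3 or higher.

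**Cost.** Up to 3 tests × 10 patients = 30 added tests per cohort, with no new visit or needle stick. Confirm with the central laboratory that the existing sample volume suffices. The review waits about one day longer, or up to three if the visit falls on Day 24. Both documents need a short edit. For completed cohorts the cost is one caveat and one summary line, drawing largely on output that SAP 8.4 already plans.
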